The HYPER study is an observational cohort study. There will be no control group, randomization, or use of placebo.

Hyperexcitability

To measure neuronal hyperexcitability in real-life settings, patients will undergo a scEEG.

Neuronal hyperexcitability will be defined as the presence of IEDs on the scEEG.

The scEEG will be inserted in the period from end of radiotherapy till first MRI evaluation after two cycles of adjuvant chemotherapy (Figure "Study flow"). Recordings from the device will start after implantation.

A specialized AI analytic software for managing long term EEG data will be used to highlight suspected IEDs that can be reviewed by a clinical neurophysiologist to determine if these episodes show epileptiform discharges^{11,12}.

Epilepsy

All patients who develop epilepsy will be treated at Rigshospitalet by [name], clinical professor in neurology with a special focus on epilepsy. Patients will be treated with standard treatment for epilepsy according to national guidelines¹³.

b. The practical implementation, examinations, and scope

Patients will be informed and included via the Department of Cancer Treatment at Rigshospitalet. Detailed inclusion process is described in section 13. The doctors and nurses at the department are experienced in including patients for clinical trials.

A neurosurgeon ([name], neurosurgeon at the Department of Neurosurgery, Rigshospitalet) will place a scEEG device under the skin behind the patient's ear closest to the tumor. The device is inserted under local anesthesia in 20 minutes. The electrodes can be inserted with different directions and will be positioned closest to the tumor.

The scEEG will be explanted after fifteen months with the possibility of extension in case the scEEG device is approved for longer implantation. The scEEG does not need to be removed before cremation.

Patients will have an extra visit at Rigshospitalet when the scEEG is implanted and one when it is explanted. Patients who develop epilepsy might have extra visits at Rigshospitalet in relation to treatment with ASM. Otherwise, there will not be extra visits needed for participation in the study.

c. Deviations from standard treatment

There will be no deviations from standard treatment both regarding tumor and epilepsy treatment.

4. Statistical considerations

a. Power analysis

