This study is explorative, and no studies have used scEEG to identify IEDs in brain tumor patients before. Therefore, making assumptions for power analysis is challenging since no data is available from similar study designs.

Our endpoints are development of epilepsy, seizure control, progression free survival and overall survival.

Based on current data from our clinical database the number of patients needed for this study is estimated to be fourteen patients. The level of significance is 2.5% one sided and the power 80%. The sample size is determined under the following assumptions: the proportion of patients having epilepsy is 50%, and the sensitivity for epilepsy with hyperexcitability is 85% or better. The null hypothesis is diagnostic accuracy = 0.5 against the alternative that diagnostic accuracy > 0.5.

5. The study participants

- a. Inclusion criteria:
 - Patients who have consented to the Neurogenom protocol¹⁴
 - Patients 18 years of age or older
 - Patients diagnosed with glioblastoma, IDH wild type grade 4
 - Patients treated with standard therapy at Rigshospitalet, Department of Cancer Treatment
 - Patient with a tumor located in a region where scEEG is expected to provide adequate signal quality
 - Performance status 0-1
 - Patients willing and able to use the scEEG, UNEEG EpiSight solution, day and night for the duration of the study
 - Patients willing and able to provide written informed consent
 - Patients able to understand the consequences of participation
 - Patients able to complete all study-required procedures, assessments and follow-up
- b. Exclusion criteria:
 - Patients who have a diagnosis of epilepsy
 - Patients treated with ASM
 - Pregnancy
 - High risk of surgical complications as assessed by the neurosurgeon
 - Involved in therapies with medical devices that deliver electrical energy into the area around the implant, such as cochlear implant(s), implantable brain stimulation and external/transcranial brain stimulation
 - Contraindications to the local anesthetic used during implantation and explantation

6. Risks, side effects, and disadvantages in the short and long term.

a. Safety measures that minimize pain, discomfort, fear, and other risks

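### Read as proportion correctly classified, the null accuracy of 0.5 is the chance value only if epilepsy or IED positivity is 50%, and the design fixes neither

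*Protocol*

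**What the plan says.** Protocol section 4a gives the study's only formal hypothesis: "The null hypothesis is diagnostic accuracy = 0.5 against the alternative that diagnostic accuracy > 0.5". The error rate and power follow from "The level of significance is 2.5% one sided and the power 80" per cent, and "the number of patients needed for this study is estimated to be fourteen patients". Two planning assumptions are given: "the proportion of patients having epilepsy is 50" per cent, and "the sensitivity for epilepsy with hyperexcitability is 85% or better". The section does not define diagnostic accuracy and gives no specificity and no expected share of IED-positive patients.

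Section 3a describes an observational cohort without a control group and makes the marker binary: "Neuronal hyperexcitability will be defined as the presence of IEDs on the scEEG". Section 5b excludes "Patients who have a diagnosis of epilepsy" and patients on anti-seizure medication, so every epilepsy case counted must arise after entry. Section 4a also concedes that "making assumptions for power analysis is challenging since no data is available from similar study designs".

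**The concern.** The natural reading of diagnostic accuracy is the share of patients whose IED status agrees with their epilepsy status. On that reading, the score of a worthless marker depends on how common epilepsy is and how common IEDs are. It is not 0.5 in general. If both are uncommon, or both are common, most patients agree by coincidence and the worthless marker scores above 0.5. If one is common and the other is not, it scores below 0.5, and an informative marker may do so too.

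The test would then respond partly to the two marginal frequencies and not only to their association. Section 2 asks how hyperexcitability is related to epilepsy and hopes to inform later trials, so a result driven by base rates would answer a different question.

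**Working it through.** **Inputs.** From section 4a: n = 14, one-sided 2.5%, power 80%, null 0.5, sensitivity 0.85, epilepsy 50%. All other epilepsy and IED rates below, and the specificity of 85%, are assumptions, because the protocol gives none.

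**1. The planned 14.** A one-sample test of 0.85 against 0.5 needs

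n = [1.960·√(0.5·0.5) + 0.842·√(0.85·0.15)]² / 0.35² = (0.980 + 0.301)² / 0.1225 = 13.39, rounded up to 14.

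So 14 fits accuracy read as proportion correct. It does not prove that reading: a two-group comparison of 85% with 15%, 7 per group, also gives 14. With 50% epilepsy and 85% sensitivity, an accuracy of 0.85 also needs a specificity of 85%, since 0.5·0.85 + 0.5·0.85 = 0.85.

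**2. Accuracy of an uninformative marker.** Let π be the epilepsy proportion and q the IED-positive proportion, independent of each other. Then

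accuracy = πq + (1−π)(1−q) = 0.5 + 0.5·(2π−1)(2q−1).

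This equals 0.5 only if π or q is 0.5. It lies above 0.5 when both are on the same side of 50%, and below 0.5 when they are on opposite sides.

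**3. Cut-offs at n = 14.** Section 4a names no test, so two are shown. The exact binomial test rejects at 12 or more correct (error 0.65% at accuracy 0.5). The large-sample z-test rejects at 11 or more: z = (11/14 − 0.5)/√(0.25/14) = 2.14, with a true error of 2.87% at accuracy 0.5.

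**4. Probability that a worthless marker is declared predictive.** Binomial tail with n = 14 and the accuracy from step 2:

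| Epilepsy π | IED-positive q | Chance accuracy | ≥12/14 | ≥11/14 |
|---|---|---|---|---|
| 50% | any | 0.50 | 0.6% | 2.9% |
| 40% | 20% | 0.08 + 0.48 = 0.56 | 2.0% | 7.3% |
| 30% | 30% | 0.09 + 0.49 = 0.58 | 2.9% | 9.6% |
| 30% | 10% | 0.03 + 0.63 = 0.66 | 9.6% | 24% |
| 70% | 90% | 0.63 + 0.03 = 0.66 | 9.6% | 24% |
| 20% | 20% | 0.04 + 0.64 = 0.68 | 12.5% | 30% |
| 30% | 70% | 0.21 + 0.21 = 0.42 | 0.1% | 0.6% |

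**5. The other direction.** Take 30% epilepsy, 100% sensitivity and 25% specificity. The marker carries information (1.00 + 0.25 − 1 = 0.25, above 0). Its IED-positive share is 0.30 + 0.70·0.75 = 82.5%, on the opposite side of 50%. Its accuracy is 0.30·1.00 + 0.70·0.25 = 0.475, on the null side of 0.5.

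**6. Power at n = 14 with 85% sensitivity and 85% specificity.** The exact binomial test against 0.5 has 64.8%. A one-sided 2.5% Fisher exact test, enumerated over all tables with the number of epilepsy cases left random, has 60% at 50% epilepsy, 45% at 30% and 27% at 20%. Its error for a worthless marker stayed below 0.6% in the scenarios checked.

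**The case against.** **The term may mean something else.** If the sponsor means balanced accuracy or the area under the ROC curve, 0.5 is the no-information value at any prevalence and the error-rate problem disappears. The sample size does not settle the reading. This stands, and it is why the point begins with the missing definition.

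**The null agrees with the plan.** Section 4a states 50% epilepsy and a null of 0.5 together, and at 50% the null is right whatever the IED rate. This also stands. A reader might infer that the null is simply wrong; the protocol does not support that. The weakness is that the stated error rate hangs on one planning value that the design does not fix.

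**The protocol does not call the epilepsy share doubtful.** Its remark on missing data concerns earlier scEEG studies in brain tumour patients, and it says the sample size draws on the department's clinical database. A reader might infer that it concedes the 50%; it does not. It also shows no figures for that share.

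**Inflation is not general.** A reader might infer that any departure from 50% makes false positives far more frequent than 2.5%. That is not so. Opposite-side departures make the test conservative, and mild same-side departures with the exact cut-off stay near or below 2.5%. Larger figures can be produced (20% epilepsy with 10% IED gives 25% and 49%; 20% with no IED in anyone gives 45% and 70%), but they need few or no IEDs. Sections 2 and 3 justify the device by its sensitivity to rare events and count any IED over a recording of up to fifteen months. If IEDs prove common and epilepsy affects fewer than half, the likelier fault is a missed signal.

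**The study is exploratory, and test details may sit in an analysis plan.** That lowers the severity. It does not remove the point, because the null, error rate and power are stated in the protocol itself.

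**Conclusion.** The point holds in limited form. Section 4a leaves diagnostic accuracy undefined. Read as proportion correct, its null of 0.5 is the chance value only if epilepsy or IED positivity is 50%. The plan meets this on paper through the assumed 50% epilepsy, but the cohort will produce its own share, and the 2.5% error rate is not protected if that share differs.

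The size depends on the assumed rates and on the cut-off. It runs from no material inflation (2.0% at 40%/20% with the exact cut-off) to 12.5% or 30% at 20%/20%. On opposite sides of 50% the error falls well below 2.5%, and an informative marker can be missed. Under balanced accuracy or AUC there is no inflation, and only the definition is lacking. Should fix.

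**What to change.** In section 4a, replace the hypothesis by one whose no-information value does not depend on prevalence. For example: the null hypothesis is sensitivity + specificity − 1 = 0 (equivalently, balanced accuracy = 0.5), tested against a positive value by a one-sided 2.5% Fisher exact test of IED status by epilepsy status; sensitivity and specificity are each reported with exact confidence intervals.

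In the same place, add the specificity assumed for planning and restate the power. At n = 14 it is about 60% with 85% sensitivity, an assumed 85% specificity and 50% epilepsy (45% at 30% epilepsy, 27% at 20%), in place of the stated 80%.

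The text change is short; its cost is this less favourable power statement. Most of the drop from 80% is not caused by the change, because the exact binomial test against 0.5 already has only about 65%. To pass 80% with the Fisher test at 50% epilepsy would take about 19 patients. The sponsor can enlarge the cohort or keep 14 and state the lower power openly. The change should be made before IED and epilepsy data are examined together, since a null altered afterwards would carry little weight.
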